### 6.6.1.2. Dose Modifications

#### 6.6.1.2.1. AM0010

Dose schedule of AM0010 may be modified for toxicity. Dose schedule reductions are defined in the protocol as follows:

Dose Schedule	Schedule Modification Criteria	AM0010
SC QD (continuous daily dosing)	-	Starting dose schedule
5 Days on/2 days off	First Grade 3 or 4 event(s)	First dose schedule reduction
4 Days on/3 days off	Second Grade 3 or 4 event(s)	Second dose schedule reduction
2 Days on/5 days off	Third Grade 3 or 4 event(s)	Third dose schedule reduction

Parameters summarized include number and percentage of patient with at least 1 dose schedule reduction and reason for dose schedule reduction, number and percentage of patients with a dose schedule reduction to 5 days on / 2 days off, number and percentage of patients with a dose schedule reduction to 4 days on / 3 days off, and number and percentage of patients with a dose schedule reduction to 2 days on / 5 days off.

Number and percentage of patients with at least 1 dose withhold and reason for dose withhold will be summarized. Number of dose withhold per patient will be summarized as well.

#### 6.6.1.2.2. Nivolumab

Nivolumab dose reductions are not permitted. A dose will be considered as actually delayed if the delay is exceeding 2 days (i.e.,  $\geq 3$  days from scheduled dosing date). Number of dose delays per patient, length of delay, and reason for delay will be summarized.

### 6.6.2. Adverse Events

Adverse event (AE) terms will be mapped using the Medical Dictionary for Regulatory Activities (MedDRA). Adverse events will be graded according to the National Cancer Institute (NCI) – A Common Terminology Criteria for Adverse Events (CTCAE) v 4.03.

Pre-existing conditions are defined as AEs that begin prior to the first dose of study drug.

A treatment emergent adverse event (TEAE) is defined as any AE that begins between the day of first dose and 30 days after treatment discontinuation (or up to any time if serious and related to study treatment), or any pre-existing condition that increases in CTCAE grade between the day of first dose and 30 days after treatment discontinuation (or up to any time if serious and related to study treatment).

Related AEs in patients treated with AM0010 in combination with nivolumab are defined as either related to AM0010 or related to nivolumab or both AM0010 and nivolumab.

The following TEAE/serious adverse events (SAE) outputs will be produced:

- a. overview of TEAEs
- b. summary of TEAEs by Preferred Terms (PTs) (all grade and grade  $\geq 3$ )
- c. summary of TEAEs by System Organ Class (SOC) and PT (all grade and grade  $\geq 3$ )
- d. summary of TEAEs by PT and Maximum Grade
- e. listing of SAEs
- f. summary of SAEs by SOC and PT (all grade and grade  $\geq 3$ )
- g. listing of TEAEs leading to study treatment discontinuation

Summaries b, c, d, and f will be produced for the related TEAEs/SAEs.

### **6.6.3. Deaths**

All deaths on study will be listed along with the cause for death.

### **6.6.4. Consolidated AEs**

Given the high level of granularity of the MedDRA dictionary, clinically identical or synonymous PTs reported under different terms in the database, in addition to being reported separately, will also be consolidated in a separate summary. The list of consolidated AE categories will be reported in the clinical study report.

### **6.6.5. Immune mediated AE**

Potential immune mediated AE, such as colitis, pneumonitis, endocrine and hepatic events will be summarized.

### **6.6.6. AE of Special Interest**

Adverse events of special interest (AESIs) are AEs thought to be potentially associated with the study treatment or the underlying disease per protocol. Therefore, aggregate or single AE terms for including additional medical interventions for identifying AEs possibly associated or possibly associated with the study drug were developed.

Adverse events of special interest are listed in the Investigator's Brochure. The Medical Dictionary for Regulatory Activities (MedDRA™) preferred terms (PTs) that are grouped under each of the AESI terms will be provided.

### **6.6.7. Clinical Laboratory Evaluation**

Summary and change from baseline by cycle will be provided for selected hematology, chemistry, coagulation tests, and thyroid function parameters.

Hematology and chemistry laboratory values will be graded according to CTCAE v4.03. The laboratory grade will be summarized by cycle and maximum post-baseline grade. Shift tables from baseline to worst post-baseline CTCAE grade will be generated.

Listing of abnormal laboratory events will be presented.

### **6.6.8. Vital Signs**

Vital signs (blood pressure, heart rate, temperature, and oxygen saturation), and weight will be summarized by cycle.

### **6.6.9. Electrocardiogram**

Electrocardiogram parameters including QTc and change from baseline will be summarized by cycle and by treatment arm. QTc will be calculated based on Fridericia's formula (QTcF). Number and percent of patients for each QTc parameter for the following categories will be summarized:

- Absolute QTc <450, 450 to <480, 480 to 500, and >500 ms
- QTc change from baseline 30 to <60 ms and  $\geq 60$  ms.

### **6.6.10. ECOG Performance Status**

European Cooperative Oncology Group performance status will be summarized by cycle.

### **6.6.11. Utilization**

Utilization data will be summarized by category across arms. The following categories will be described:

- transfusions (on study treatment and during short-term follow up)
- hospitalizations (on study treatment and during short-term follow up)

For categorical variables, frequency and the corresponding proportions will be calculated.

## **6.7. Exploratory Analysis**

### **6.7.1. Pharmacokinetic Analysis**

Serum concentration data will be summarized. Descriptive statistics will include mean, median, range, and SD, as appropriate.

Additional PK and/or PK/pharmacodynamic (PD) analyses may be conducted at interim as well as on final data. These will be specified in a separate PK/PD analysis plan.

### **6.7.2. Biomarker Analysis**

Biomarker analyses will be described separately.

### **6.7.3. Immunogenicity Analysis**

The Treatment Emergent (TE) ADA evaluable population will be defined within the Safety Population as those patients with both a baseline ADA test result and a postbaseline ADA test result. As a proportion of the TE ADA evaluable population, the number and frequency of the following will be tabulated by treatment group: TE ADA+ patients, and TE ADA+ patients with

detected higher-tier assay results. Included in the same tabulation will be, as a proportion of the TE ADA evaluable population, the number and frequency of patients with ADA present at baseline, as well as patients with detected higher-tier assay results at baseline.

A summary will be provided of the number and percentage of patients who receive AM0010 reporting specific TEAEs (overall and by PT) by patient TE ADA status (TE ADA+, TE ADA-, TE ADA Inconclusive, Patient not evaluable for TE ADA). The PT will be ordered by decreasing frequency in the TE ADA+ status group. The specific TEAE of interest are events in any one of the MedDRA Anaphylactic reactions Standardized MedDRA Query (SMQ), Hypersensitivity SMQ, Angioedema SMQ, Injection site reactions High Level Term (HLT), or Infusion site reactions HLT.

Additional immunogenicity analyses, to be presented in a standalone immunogenicity report in context with other studies of AM0010, will be described in a separate SAP.

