### **7.13 Immunogenicity (Anti-Drug Antibodies)**

Blood samples for immunogenicity analysis will be obtained on all patients on Arms 1 and 2 (including crossover patients). Samples will be evaluated for development of ADAs by a validated immunoassay.

The ADA samples will be drawn pre-dose (AM0010 and nivolumab):

- Day 1 of Cycles 1, 2, 3, 4, and every fourth cycle thereafter (eg, 8, 12, 16, etc.).
- End-of-treatment visit
- Safety observation visits 60 and 90 days after the last dose of study treatment.

For the sample collection during continued-access period, refer Section 3.7 and [Appendix B](#).

All immunogenicity samples will be retained for a maximum of 15 years after the last participant visit, or for a shorter period if local regulations and Ethical Review Boards (ERBs) allow, at a facility selected by the sponsor. The duration allows the sponsor to respond to future regulatory requests related to the investigational product. Any samples remaining after 15 years will be destroyed.

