### **6.1.2. Definitions and Conventions**

Study treatment refers to AM0010 + nivolumab or nivolumab.

The date of randomization is the date the patient was randomly assigned to AM0010 + nivolumab arm or nivolumab arm using the IWRS.

The date of **first** dose is the date of the first dose of any study treatments.

The baseline value of a safety assessment is the last value observed prior to the date of first dose.

The study day of a safety event or assessment will be calculated as:

- The difference between the date of the event or assessment and the date of first study dose plus 1 for all events or assessments occurring on or after the day of first dose. For example, if an event occurs on 08 June 2018 and the date of first dose was 06 June 2018, the study day of the event is 3.
- The difference between the date of the event or assessment and the date of first dose for all events or assessments occurring before the day of first dose. For example, if an event occurs on 05 June 2018 and the date of first dose was 06 June 2018, the study day of the event is -1.

The study day of an efficacy event or assessment will be calculated as:

- the difference between the date of the event or assessment and the date of randomization plus 1 for all events or assessments occurring on or after the date of randomization.
- the difference between the date of the event or assessment and the date of randomization for all events or assessments occurring before the date of randomization.
- 1 month = 30.4375 days
- 1 year = 365.25 days

Unless otherwise noted, summaries of continuous variables will include a mean, median, standard deviation (SD), minimum, and maximum.

Unless otherwise noted, summaries of categorical variables will include the frequency and percentage (relative to the population being analyzed) of each category.

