#### **6.7.4. Crossover Patients**

Patients in Arm 2 (nivolumab) who crossover to Arm 1 (AM0010 in combination with nivolumab) following documented disease progression will be analyzed accordingly if data warrants.

For patients who crossover to Arm 1 after documented disease progression on nivolumab, time to progression while on nivolumab and time to progression following progression will be estimated, where the time to progression following crossover is defined as the time from time of crossover to the earliest documented disease progression. The last available tumor assessment before crossover will serve as the baseline for disease assessment post crossover. If the number of events permits, time to progression before and after crossover will be summarized descriptively using the Kaplan-Meier method

Patients who crossover to the AM0010 in combination with nivolumab are censored at time of crossover (i.e., AEs occurring during treatment with AM0010+nivolumab are excluded for control arm (nivolumab) patients). An exploratory safety analysis may be conducted for the crossover patients including all adverse events starting from the date of first dose of AM0010+nivolumab.

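### The SAP's table of hypersensitivity-type events by anti-AM0010 antibody status ignores event order and time at risk, and does not say how crossover patients enter it

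*SAP*

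**What the plan says.** SAP 6.7.3 (Immunogenicity Analysis) plans one table relating antibodies to reactions: the "number and percentage of patients who receive AM0010 reporting specific TEAEs (overall and by PT) by patient TE ADA status". The events are those in the anaphylaxis, hypersensitivity and angioedema queries and the injection-site and infusion-site reaction terms. The status groups are "TE ADA+, TE ADA-, TE ADA Inconclusive, Patient not evaluable for TE ADA". Evaluable patients are "those patients with both a baseline ADA test result and a postbaseline ADA test result", with no condition on when the post-baseline result was obtained. Further immunogenicity analyses are left to a separate SAP.

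Four other provisions determine what the table counts:

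- **Sampling.** Protocol 7.13 draws ADA samples before dosing on Day 1 of Cycles 1 to 4, then at every fourth cycle, at end of treatment, and at the "Safety observation visits 60 and 90 days after the last dose of study treatment". Both arms and crossover patients are sampled.
- **Event window.** SAP 6.6.2 defines a TEAE as "any AE that begins between the day of first dose and 30 days after treatment discontinuation", extended without limit only for serious, related events. Worsening pre-existing conditions have the same window.
- **Start of the window.** Under SAP 6.1.2 the date of first dose "is the date of the first dose of any study treatments".
- **Crossover.** SAP 6.7.4 censors crossover patients at crossover, so that "AEs occurring during treatment with AM0010+nivolumab are excluded for control arm (nivolumab) patients".

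**The concern.** A status fixed over the whole study is set against events spread over that study. No event date, date of first positive sample or time at risk enters the table.

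1. **Order and exposure.** A reaction in the first cycle of a patient who turns positive months later is displayed as a TE ADA+ reaction. Because treatment length varies, time on treatment drives both the chance of a positive sample and the chance of a reaction.
2. **Crossover.** An Arm 2 patient who crosses over is a patient who receives AM0010, but the general window and exclusion rules were not written with this table in mind.

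This is the only analysis in this SAP that relates anti-AM0010 antibodies to reactions, so readers will use it to judge whether antibodies matter for safety. It could suggest an antibody effect that is absent. For crossover patients it could also leave out the reactions that matter most.

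**Working it through.** The plan gives no figure on this point to reproduce. The check is a reading of the rules together, followed by a calculation in which antibodies and reactions are truly unrelated.

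**Order.** Cycles last 4 weeks (Protocol Appendix A), so the first scheduled post-baseline ADA sample is on day 29. On-treatment samples are then 4 weeks apart up to Cycle 4 and 16 weeks apart afterwards. A patient first positive 60 or 90 days after the last dose can have no non-serious TEAE after that sample, because the general window closes at 30 days. All such events in that patient precede detection, yet are counted under TE ADA+.

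**Null calculation.** Assumptions:

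- Treatment time is exponential with rate λ. The median is anchored on the median PFS of 2.3 and 3.5 months for nivolumab in Protocol 1.1, with 6 months as an upper value.
- Antibody onset (rate a) and first reaction (rate r) are independent exponential times. The documents give neither rate for this trial.
- Reactions count up to 30 days after the last dose. In the first set of runs, antibody onset occurs only up to the last dose.

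Then:

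- P(never ADA+) = λ/(λ+a)
- P(no reaction) = e^(−30r) · λ/(λ+r)
- P(neither) = e^(−30r) · λ/(λ+a+r)
- P(reaction | ADA−) = 1 − P(neither)/P(never ADA+)
- P(reaction | ADA+) = [1 − P(no reaction) − P(never ADA+) + P(neither)] / [1 − P(never ADA+)]

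Example: median 3.5 months, mean antibody onset 120 days, mean time to reaction 300 days.

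- λ = ln 2/(3.5 × 30.4375) = 0.006507 per day; a = 1/120; r = 1/300
- P(never ADA+) = 0.43845; P(no reaction) = 0.90484 × 0.66124 = 0.59832; P(neither) = 0.90484 × 0.35803 = 0.32396
- P(reaction | ADA−) = 1 − 0.32396/0.43845 = 26.1%
- P(reaction | ADA+) = 0.28719/0.56155 = 51.1%
- Risk ratio = 1.96, with no true association

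Simulation of 400,000 patients per scenario on the protocol's sampling schedule agrees with this. The results are:

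| Null scenario | Table risk ratio | TE ADA+ patients' reactions before first positive sample |
|---|---|---|
| Constant rates; onset mean 120 or 240 days, reaction mean 300 or 600 days; median 2.3, 3.5 or 6 months (12 runs) | 1.69–2.56 | 40–58% |
| Constant rates; onset 5–10% and reactions 3–6% per month; median 2.5–6 months; onset may continue to 90 days after last dose | 1.4–1.9 | 54–72% |
| Equal treatment duration | 1.00 | 51% |
| Reactions early (30% of patients, mean 10 days) | 1.01 | 98% |
| Every reaction stops treatment | 1.01 | 22–27% |

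In the second row, P(never ADA+) and P(neither) are multiplied by e^(−90a). In the 12 runs of the first row, splitting reactions and person-time at antibody onset gives a rate ratio of 1.00 to 1.01. The excess in the table is therefore due to unequal time at risk.

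**Crossover rules side by side.** The table takes patients who receive AM0010, which literally includes crossover patients. Their window opens with the first nivolumab dose (6.1.2, 6.6.2). Their events on AM0010 plus nivolumab are excluded (6.7.4), and no exception is stated for this table. What remains is the nivolumab-alone period. No ADA baseline at the start of AM0010 is stated either, so a crossover patient could be evaluable on samples all taken before any AM0010. In Arm 1 this cannot arise, because AM0010 is given first (Protocol 6.1).

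The crossover rate is not in the documents. If crossover patients numbered 20%, 40% or 60% of Arm 1 (assumption; rates as in the example), 15%, 25% or 34% of the counted reactions would precede any AM0010.

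**The case against.** **Misordering does not by itself create a false association.** A reader might infer that counting reactions from before the antibody is what produces the excess. The last three rows of the table show otherwise: many or most reactions precede detection there, yet the ratio is about 1.0. The distortion needs unequal time at risk and reactions that go on occurring without ending treatment. Treatment to progression supplies the first condition; the documents do not say how reactions are distributed in time. This objection stands and limits the claim to what the table can show.

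**The numbers are soft.** Both rates are assumed, and Protocol 1.2.2.3.2 reports no high-titre antibodies in the patients tested. With 25 patients in Arm 1, the example amounts to about 14 positive and 11 negative patients (0.56 × 25), with roughly 7 and 3 reactions. Chance variation at that size is large. This also stands, and it is a reason to show dates rather than percentages alone.

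**Crossover patients may not be meant.** SAP 6.7.4 censors them and Table JZGD.6.2 leaves the crossover period out of cumulative dose, so an Arm 1 table may be intended. SAP 6.7.4 also allows a safety analysis from the first combination dose, but it is optional and not by antibody status. A reader might infer that a definite share of AM0010 recipients is counted over the wrong period. The documents do not support any such figure, since neither inclusion nor the crossover rate is settled.

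**The stakes are limited.** The table is exploratory and descriptive, and the separate immunogenicity SAP may deal with timing. That document is not available here, and this table would be produced as written in any case.

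**Person-time rates are not a safe substitute.** Antibody-positive time is late time by construction. With early reactions (25% of patients, mean onset 20 days, no true association), splitting person-time at the first positive sample gives a rate ratio of 0.04 to 0.09, a false protective effect. With constant rates it gives 0.63 to 0.90 if person-time is not stopped at the first event.

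**Conclusion.** The point holds in a limited form. The table mixes reactions from before and after antibody detection under one label. Under treatment to progression it can show an excess in TE ADA+ patients when antibodies and reactions are unrelated. The illustrative risk ratio is about 1.4 to 1.9, and up to 2.6 under other assumed rates, when reactions occur at a constant rate. It is about 1.0 when they are early, when durations are equal, or when each one stops treatment. Across all of these scenarios, 22% to 98% of the reactions shown for TE ADA+ patients precede the first positive sample.

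Read literally, the rules also count only the period before AM0010 for crossover patients; the number affected is not known. It would go too far to say that the table will show a false association, or that any efficacy result is touched. The matter concerns the interpretation of one exploratory safety table, but correcting it is cheap.

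**What to change.** Amend SAP 6.7.3 as follows.

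1. **Crossover.** State whether crossover patients are in this table. If they are, count only events with onset on or after the first AM0010 dose, include their events on AM0010 plus nivolumab as a stated exception to 6.7.4, and take the ADA baseline as the last sample before the first AM0010 dose. If they are not, say that the table is limited to Arm 1.
2. **Order.** For TE ADA+ patients, show events with onset before, and on or after, the first TE ADA+ sample. Add a listing of event onset dates, ADA sample dates and results, and treatment duration.
3. **Rates, if wanted.** Give exposure-adjusted rates only as a supplement, with person-time stopped at the first event and a note that antibody-positive time is later time by construction. Stopping person-time does not remove the false protective effect when reactions are early.

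The cost is a few sentences, extra columns and one listing; no new data are needed. The downsides are small cells and a seroconversion date known only to the sampling interval, which is 4 to 16 weeks on treatment.

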#### **6.7.4. Crossover Patients**

Patients in Arm 2 (nivolumab) who crossover to Arm 1 (AM0010 in combination with nivolumab) following documented disease progression will be analyzed accordingly if data warrants.

For patients who crossover to Arm 1 after documented disease progression on nivolumab, time to progression while on nivolumab and time to progression following progression will be estimated, where the time to progression following crossover is defined as the time from time of crossover to the earliest documented disease progression. The last available tumor assessment before crossover will serve as the baseline for disease assessment post crossover. If the number of events permits, time to progression before and after crossover will be summarized descriptively using the Kaplan-Meier method

Patients who crossover to the AM0010 in combination with nivolumab are censored at time of crossover (i.e., AEs occurring during treatment with AM0010+nivolumab are excluded for control arm (nivolumab) patients). An exploratory safety analysis may be conducted for the crossover patients including all adverse events starting from the date of first dose of AM0010+nivolumab.

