## **7.8 Continued Treatment**

### **7.8.1 Crossover**

At the time of disease progression (as assessed by the Investigator) patients randomized to trial Arm 2 may crossover to study Arm 1 to receive AM0010 and nivolumab. When progressive disease is noted on the scan for an ARM 2 patient, no more than 21 days should pass before the patient crosses over to ARM 1. The scans and/or clinical assessment at crossover will be used as a new baseline to determine response or PD on ARM 1.

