## 5.2. Determination of Sample Size

Approximately 50 patients will be randomized to the 2 treatment arms in a 1:1 ratio. With a total of 50 patients, 25 patients each arm would enable evaluating ORR for each treatment arm. With 25 patients in each treatment arm, the 90% confidence interval (CI) for an objective response rate would be (3%, 28%) if 3 patients (12%) had a response; (11%, 42%) if 6 patients (24%) had a response; and (17%, 50%) if 8 patients (32%) had a response.

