### **6.5.3. Secondary Endpoints**

#### **6.5.3.1. Progression-Free Survival**

##### **6.5.3.1.1. Definition**

Progression-free survival (PFS) is defined as the time from randomization to the date of documented progression (per scan or clinical progression as determined by the investigator) or the date of death due to any cause, whichever is earlier.

The detailed censoring rules are described in [Table JZGD.6.1](#).

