#### **6.8. Timing of Planned Analyses**

Interim analysis may be conducted to evaluate patient's safety. Efficacy data will be described without performing any formal statistical test. The primary analysis (data cut off) will occur 6 months after the last patient randomized.

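### The before/after time-to-progression summary in crossover patients (SAP 6.7.4) sets two differently selected and censored times side by side, with death not an event, and cannot be interpreted in either direction

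*SAP*

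**What the plan says.** SAP 6.7.4, within the exploratory analyses of Section 6.7, covers Arm 2 patients who move to the combination after progression. It applies if the data warrant it. The analysis set is fixed by the opening of its second paragraph: "For patients who crossover to Arm 1 after documented disease progression on nivolumab". Two times are then estimated, one on nivolumab and one afterwards, and "the time to progression following crossover is defined as the time from time of crossover to the earliest documented disease progression". The output is given as: "If the number of events permits, time to progression before and after crossover will be summarized descriptively using the Kaplan-Meier method".

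Death is not mentioned in that definition. The PFS definition in SAP 6.5.3.1.1 does include it: "or the date of death due to any cause, whichever is earlier". Table JZGD.6.1 gives censoring rules for PFS only, and none are given for the crossover times.

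On timing, SAP 6.8 says: "The primary analysis (data cut off) will occur 6 months after the last patient randomized". Protocol 3.6 places study completion after 3 years of survival follow-up from the last randomization.

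Protocol 7.8.1 adds: "The scans and/or clinical assessment at crossover will be used as a new baseline to determine response or PD on ARM 1". SAP 6.7.4 lists no post-crossover response output.

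**The concern.** The two times come from the same patients, but they are selected and censored differently.

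- **Before crossover.** A patient enters only by progressing on nivolumab, alive and before the data cut. Patients who died first, or who had not progressed by the cut, are absent. Every time is therefore an observed event, and long times are under-represented.
- **After crossover.** Times are ordinary right-censored times. Because death is not an event, the usual Kaplan-Meier handling would censor a patient who dies without documented progression, although the SAP does not say so.

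Under a constant progression hazard both features make the post-crossover curve look longer. This is the only efficacy output that the SAP specifies for AM0010 added after nivolumab failure, and Section 6.7.4 carries no caveat. A reader shown the two medians could credit AM0010 with a gain produced by the way the patients and events were chosen.

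**Working it through.** The SAP states no figure for this analysis. Its only design figures, the 90% intervals for ORR with 25 patients per arm, reproduce (3/25 gives 3.4%-28.2%, 6/25 gives 11.0%-42.0%, 8/25 gives 17.0%-50.4%) but say nothing about crossover patients. The check is what the two curves would show if AM0010 had no effect.

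**Inputs from the documents**
- Nivolumab median PFS m: 2.3 months (non-squamous) and 3.5 months (squamous), Protocol 1.1.
- Data cut: 6 months after the last randomization (SAP 6.8); 36 months as the later look (Protocol 3.6).

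**Assumptions not in the documents**
- Exponential times.
- Uniform accrual over A = 12 months (6 months as a check).
- A share d of first PFS events are deaths: 10-30%.
- Progression hazard after crossover equal to that before, then multiplied by f = 1.25 and 1.5.
- The gap of up to 21 days between progression and crossover is ignored here.

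**Step 1: pre-crossover median.** Let λ = ln 2 / m be the total hazard. Among patients whose first event is progression, times are exponential with hazard λ, because death has already removed slow progressors. Truncation at the cut shortens them further. With follow-up uniform on 6 to 18 months:

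P = 1 − (e^(−6λ) − e^(−18λ)) / (12λ), and the median is −ln(1 − P/2) / λ.

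- m = 2.3: λ = 0.3014, P = 0.956, median 2.16 months.
- m = 3.5: λ = 0.1980, P = 0.884, median 2.94 months.

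**Step 2: post-crossover median.** With death censored, Kaplan-Meier follows the progression hazard λ(1 − d) alone, so the median is m / (1 − d).

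**Step 3: null ratio, after/before.**

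| d | m = 2.3, 6-month cut | m = 3.5, 6-month cut | 36 months (both) |
|---|---|---|---|
| 0% | 2.30/2.16 = 1.07 | 3.50/2.94 = 1.19 | 1.00 |
| 10% | 2.56/2.16 = 1.18 | 3.89/2.94 = 1.32 | 1.11 |
| 20% | 2.88/2.16 = 1.33 | 4.38/2.94 = 1.49 | 1.25 |
| 30% | 3.29/2.16 = 1.52 | 5.00/2.94 = 1.70 | 1.43 |

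Ratios use unrounded medians. By 36 months truncation has effectively gone and the ratio is 1/(1 − d). With 6-month accrual the 6-month-cut ratios for d = 10-30% are 1.24-1.60 and 1.46-1.87. A separate simulation of 200,000 patients per scenario, including the 21-day gap, gave 1.20, 1.34, 1.54 and 1.33, 1.51, 1.71 for d = 10%, 20%, 30% with 12-month accrual.

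**Step 4: faster natural progression after nivolumab failure.** The post-crossover median becomes m / (f(1 − d)), so the break-even f equals the null ratio in Step 3. At d = 20% and the 6-month cut, f = 1.25 leaves 1.07 and 1.19, and f = 1.5 gives 0.89 and 0.99. At 36 months, f = 1.25 already gives 1.00.

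**Step 5: counting death after crossover.** If progression and death hazards are unchanged, the total hazard is λ again and the median returns to 2.3 or 3.5 months. If post-crossover death is instead taken from the crude difference of OS and PFS medians (12.2 − 2.3 = 9.9 and 9.2 − 3.5 = 5.7 months), simulation at d = 15% gives 2.11 and 2.37 months, that is 0.99 and 0.81 of the pre-crossover medians. The post-crossover endpoint is then well defined, but the pre-crossover set still contains no deaths, so the contrast remains unusable.

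**Step 6: size of the data.** With about 25 patients in Arm 2, 60% uptake (assumed) and d = 15%, simulation expects about 11-12 crossover patients and 5-8 post-crossover progressions. With no drug effect and equal hazards, the post-crossover median is the longer one in 65% (m = 2.3) and 71% (m = 3.5) of trials. At f = 1.5 this falls to 36% and 47%.

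**The case against.** The strongest reply is that the direction is not established. The excess requires an unchanged progression hazard after nivolumab failure, and the documents report only first-event PFS and OS. Step 4 shows that a modest acceleration removes it. A reader might infer that an inert AM0010 would be bound to look beneficial; the documents do not support that. This part of the objection stands, and it limits the point to comparability.

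Second, the SAP plans no formal comparison. The summary is exploratory, conditional on the data and on the number of events, and has no test, ratio or decision rule. A reader might infer that the sponsor intends to claim that AM0010 overcomes nivolumab resistance, but nothing in the SAP says so. This also stands and lowers the weight of the point. It does not remove it: SAP 6.1.1 makes all analyses descriptive, so the label does not tell a reader to discount this one.

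Third, the percentages are large-sample values from continuous times. With so few events, noise dominates a single trial. With 8-week scans the simulated median ratio at d = 15% is 1.00 for m = 2.3 and 1.50 for m = 3.5, although 6-month restricted means still lean towards post-crossover (3.42 vs 3.82 and 3.84 vs 4.38 months). The percentages therefore show the order of the bias and do not predict what this trial would report.

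Fourth, SAP 6.8 ties the 6-month cut to the primary analysis and not expressly to 6.7.4. If the summary is produced only at the end, the 36-month figures apply.

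Finally, death is omitted from the definition and not expressly excluded. Its handling is therefore unspecified, which is itself a gap to close.

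**Conclusion.** The point holds in a limited form. As written, the pre- and post-crossover Kaplan-Meier curves are selected and censored differently, and the post-crossover endpoint does not count death. Under a constant progression hazard and no drug effect, the post-crossover median is longer by about 18-70% at the 6-month cut and 11-43% at 36 months, for 10-30% of first events being deaths, 12-month accrual and the protocol's own nivolumab medians. The break-even acceleration is about 1.25-1.5 for death shares of 15-20% at the 6-month cut. It is higher with more deaths (1.70 at 30% with m = 3.5) and lower at later cuts. Since the documents give neither the natural post-progression rate nor the death share, a longer or a shorter post-crossover time would say nothing reliable about AM0010. The randomized primary and secondary analyses are not affected.

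**What to change.** In SAP 6.7.4:

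1. Define the post-crossover endpoint as PFS from the first crossover dose, with death from any cause as an event, and apply the censoring rules of Table JZGD.6.1 from the crossover baseline.
2. If pre-crossover times are still shown, present them as a description of who crossed over, not as a comparator.
3. State that no inference about AM0010 will be drawn from the before/after contrast.
4. In the same edit, correct the phrase that describes the second time as following progression where crossover appears to be meant. Also reconcile the baseline: SAP 6.7.4 uses the last tumor assessment before crossover, while Protocol 7.8.1 uses scans and/or clinical assessment at crossover.

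Post-crossover response against the Protocol 7.8.1 baseline, with an exact confidence interval, is an optional addition.

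The cost is SAP wording and a small programming change on data already collected. The downside is that the post-crossover result will look less favourable than under the present definition.
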